The primary endpoints will be changes in physical activity levels and healthy diet score from baseline to 3-month follow-up. Physical activity levels will be quantified based on survey responses to the following questions: (1) "In the last 3 months, how many times per week did you perform aerobic exercises?" and (2) "In the last 3 months, how many times per week did you perform strength training?" These two questions align with recommendations from the Canadian Physical Activity Guidelines, which split exercise into the two domains of aerobic exercise (150 minutes of moderate to vigorous activity per week) and strength training (2x per week). Dietary healthiness will be ascertained using the dietary risk score developed by the INTERHEART study which was found to explain 30% of the population attributable risk for acute myocardial infarction¹⁰. Briefly, the dietary risk score takes into account consumption of meat, salty snacks, fried foods, fruits and vegetables. Secondary endpoints will include cardio-metabolic markers (triglycerides, C-reactive protein, fasting glucose, blood pressure), measures of fitness (waist-to-hip ratio, circumference of thigh, calf, and bicep, body fat percentage) and cardio-metabolic risk as estimated by the validated INTERHEART modified risk score (IHMRS)¹¹.

Measurements and measurement instruments

a) Fitness and Physiologic Measurements

The same measurements will be taken at baseline and at 3-month follow-up (Table 2).

Table 2. Fitness and physiologic attributes and the corresponding measurement device.

Measurement(s)	Device
Systolic & Diastolic Blood Pressure	Sphygmomanometer
Resting Heart Rate	Stopwatch/Timer
Body Fat Percentage	Scale
Weight	Scale
Waist-to-Hip Ratio	Myotape measure
Circumference of thigh, calf, bicep, neck, and shoulder span	Myotape measure

b) Blood Collection & Laboratory Testing

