All analyses conducted will follow the “Intention-to-treat” (ITT) principle to avoid biases due to differential adherence or loss-to-follow-up. In other words, no post-hoc exclusions will be made; study participants will be analyzed according to the group to which they were initially assigned even if they did not receive the intended treatment (e.g. due to injury during trial period impeding ability to exercise) or did not comply. Descriptive characteristics of each group will be summarized as the mean, standard deviation and 95% confidence-interval for continuous variables and using frequencies and percentages for categorical variables. Statistical tests will be two-sided, and between-group comparisons will be presented with 95% confidence intervals where possible. The statistical significance level set will vary depending on the number of statistical tests performed. Multiple hypotheses testing will be adjusted for within analyses of primary and secondary endpoints using a Bonferroni-corrected p-value threshold.

Baseline characteristics

Baseline characteristics will be compared using univariate regression to assess the balance of key risk factors between the intervention and control groups. Linear regression will be applied for continuous variables (age, blood pressure, waist-to-hip ratio, body fat percentage, total weekly

physical activity level, and dietary risk score) logistic regression for dichotomous variables (gender, smoking status, diabetes, dyslipidemia), and analysis of covariance (ANCOVA) will be applied for categorical variables exceeding two factor levels (ethnicity, hospital site). Intervention status will be the independent variable in the regression model. Differences in the mean or proportion of categories between groups will be considered statistically significant if the P-value is less than 0.05.

Primary Endpoints

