The primary endpoints are changes in physical activity levels as well as dietary risk score (DRS) from baseline to follow-up. Between-group differences in primary endpoints will be evaluated through linear regression. Weekly physical activity level will be represented as a continuous variable (frequency of strength training and aerobic exercise per week) for the primary analysis. Baseline characteristics found to be differentially distributed between intervention and control groups will be included as covariates in subsequent models. Between-group differences for changes in dietary risk score will be assessed through linear regression again adjusting for covariates. The significance threshold for physical activity levels and dietary health will be 0.025 given that two primary endpoints are tested.

Subgroup analysis will be conducted to explore whether changes in dietary health and physical activity levels differ based on key strata (age > 40 vs. age < 40, ethnicity, gender, baseline low/med/high physical activity levels and baseline dietary risk score tertiles). For example, it is conceivable that individuals who begin with the lowest activity levels and least healthy diets have the derive more benefit from personalized health recommendations, whereas others who already adhere to healthy lifestyle behaviours may have an attenuated response to our intervention.

Secondary Endpoints

Between-group differences in changes in levels of dyslipidemia (triglycerides), dysglycemia (fasting glucose), inflammation (C-reactive protein), blood pressure, measures of fitness (waist-to-hip ratio, circumference of thigh, calf, and bicep, body fat percentage) and overall cardio-metabolic risk as estimated by IHMRS will be analyzed using linear regression. Model covariates will include any baseline characteristics found to be differentially distributed between intervention and control groups. These analyses are considered exploratory and the significance threshold will thus be set at 0.05 for suggestive association and 0.005 (i.e. Bonferroni correction for 10 tests) for definitive association.

Technical Considerations

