All statistical analyses will be conducted in R version 3.4.0. Outlying values exceeding four standard deviations will be winsorized or removed if due to a data entry error. If a continuous variable is not normally distributed, then log transformation or quantile normalization will be applied. Missing values for continuous variables will be imputed based on the mean value across all samples with non-missing values including both intervention and control groups. For categorical variables, missing values will be imputed using the proportion of non-missing samples belonging to a given factor level to define the probability of assigning a study participant to that factor level.

Power Calculations

At a sample size of 500 participants (250 intervention and 250 control group), we estimate that we will have 90% power to detect a difference of 0.32 standard deviations between intervention

and control groups ($\alpha=0.025$). An alpha of 0.025 is used in lieu of the traditional value of 0.05 in order to account for multiple hypotheses testing of the two primary endpoints (physical activity and diet risk score). For physical activity, this is equivalent to a difference in ~ 50 MET-min/wk which translates to a difference of 12.5 minutes of moderate exercise or 6.75 minutes of vigorous exercise per week⁹. This power calculation is based on the work by Jurakic *et al.* (2009) who estimated average weekly physical activity levels in adult Croatians to be 3492 MET-min (SD=162.25) using the same validated questionnaire that will be used in the present trial¹². The translation of the dietary risk score is less straight-forward as the scoring system is comprised of disparate food habits that best predict acute myocardial infarction (e.g. salty meat vs. cooked vegetables). Granted, we will be well-powered to detect a 0.32 standard deviation in INTERHEART dietary risk score between intervention and control groups at $\alpha=0.025$.

Data Security & Privacy

Primary genetic data is defined as an individual's genotypic state generated directly from a laboratory instrument. Primary genetic data is highly sensitive personal information as it represents an individual's genetic code. Consequently, strict security measures will be employed to safeguard these data and mitigate the risk of confidentiality breach:

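### Does the general rule for transforming non-normal variables leave the primary analysis open to choice?

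*Combined protocol and SAP*

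**What the plan says.** The rule is one sentence in Technical Considerations, placed among winsorising and imputation: "If a continuous variable is not normally distributed, then log transformation or quantile normalization will be applied".

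Under Primary Endpoints, "The primary endpoints are changes in physical activity levels as well as dietary risk score (DRS) from baseline to follow-up", and both are analysed by linear regression. For activity the plan adds: "Weekly physical activity level will be represented as a continuous variable (frequency of strength training and aerobic exercise per week) for the primary analysis". The list of continuous variables under Baseline characteristics includes weekly activity and the dietary risk score.

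The test level is also stated: "The significance threshold for physical activity levels and dietary health will be 0.025 given that two primary endpoints are tested". Under Overview, tests are two-sided, analysis is by intention to treat, and "between-group comparisons will be presented with 95% confidence intervals where possible".

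Power Calculations claims "90% power to detect a difference of 0.32 standard deviations" for 250 per arm. Of the diet endpoint it says: "The translation of the dietary risk score is less straight-forward".

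**The concern.** Read literally, the rule reaches every continuous variable, and so apparently both primary endpoints. Three decisions are then unwritten:

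- what counts as non-normal;
- whether the value at each visit or the change is transformed;
- which of the two transformations is used.

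The log also does not fit. It is undefined for a change of zero or less, and for zero sessions per week if visit values are logged. The survey questions under Endpoints allow zero, and no offset is given.

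If these decisions were made with results in view, the error rate could exceed 0.025. The options also estimate different quantities. After quantile normalisation, the activity effect and its interval are in normal-score units, not sessions per week.

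**Working it through.** **1. The plan's own figure.** Inputs from Power Calculations: 250 per arm, difference 0.32 SD, alpha 0.025; two-sided from Overview.

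Power = Φ(0.32 × √(250/2) − z₀.₉₈₇₅) = Φ(3.578 − 2.241) = Φ(1.336) = 0.909.

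The stated 90% is reproduced, and the same formula needs 243 per arm. The transformation rule does not affect this figure.

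**2. What the rule permits for activity.** If changes were normal with mean m SD, the share at or below zero is Φ(−m): 50% at m = 0, 37% at 0.32, 31% at 0.5 and 16% at 1. The log of the change is therefore unavailable for a large share of participants. The log of visit values fails at zero sessions (2-33% of participants at baseline under the counts assumed below). Three analyses remain:

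- the untransformed change, if it is judged normal enough;
- the quantile-normalised change;
- the difference between quantile-normalised visit values.

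**3. Assumptions for the simulations.** The documents give no distribution of sessions per week, so these results are illustrations. Counts were gamma-Poisson with a shared person-level rate: mean 1.5, 3, 4 or 6 sessions, shape 2 or 5, rise of 20% or 50% (4 × 2 × 2 = 16 scenarios). Each trial had 250 per arm and a two-sided t test at 0.025. Quantile normalisation used rank-based normal scores. There were 20,000 trials per scenario, so the Monte Carlo standard error is √(0.025 × 0.975/20,000) ≈ 0.001.

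**4. Does the criterion matter?** Yes. Shapiro-Wilk rejected normality of the integer changes in every trial, whereas absolute skewness above 1 occurred in 0-42%. The unwritten criterion decides whether the rule applies.

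**5. Error rate at nominal 0.025.**

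| Analysis or way of choosing | Error rate |
|---|---|
| Untransformed change | 0.0240-0.0267 |
| Normalised change | 0.0237-0.0269 |
| Visit values normalised, then differenced | 0.0235-0.0261 |
| Untransformed or normalised change, chosen by pooled skewness above 0.5 (5,000 trials per scenario) | mean 0.0255; untransformed alone 0.0252 |
| Smaller p-value of untransformed or normalised change | 0.0259-0.0307 |
| Smaller p-value of normalised change or normalised visit values | 0.0280-0.0387, mean 0.0332 |

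A separate run of six scenarios (6,000 trials each, standard error about 0.002) gave 0.021-0.028 for single analyses, 0.019-0.027 for the arm-blind skewness check, and 0.030-0.035 for the smaller of the last two p-values. For a near-normal score, as the dietary score might be, taking the smaller p-value gave only 0.028-0.030.

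**6. Power at a true difference of about 0.32 SD** (24 assumed scenarios, 3,000 trials each). Untransformed change: 90-92%. Normalised change: 89-97%. Normalised visit values: 79-90% for a proportional effect, 88-99% for an additive one. Against the normalised change, the untransformed change was 1-2 points better with a proportional effect and no extra tails. It was 6 points worse with heavy tails and an additive effect (91% against 97%). Another heavy-tailed variant gave 0.899 against 0.984, a loss of 8.5 points.

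**The case for a change.** The strongest argument needs no misconduct. Two competent analysts could read the rule differently, one normalising changes and the other visit values. With a proportional effect of about 0.32 SD, these two analyses disagreed on significance in 9-13% of simulated trials. Study Design says the study team does not know the allocation, but nothing says that the transformation decision is taken blind. One sentence would remove the ambiguity.

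It stands that the text is incomplete and that the criterion could decide which analysis is run. Less follows from this than appears:

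- Coverage of the primary endpoints is an inference. The rule sits among data-preparation steps, the variables listed under Baseline characteristics are levels rather than changes, and Primary Endpoints names frequency per week as the scale for activity. An analyst could take that specific statement to govern.
- Disagreement between two valid analyses of the same data is expected. It shows that they differ in power, not that either is wrong.
- A larger illustration, in which at least one of five scales rejected in 4.6% of null trials, includes two logs with an added constant. The rule offers no such log.
- The simulations omit winsorising at four SD, the step just before the rule. In one re-run it cut the highest rate of absolute skewness above 1 from 0.38 to 0.19, so the trigger rates are likely overstated.
- Loss of natural units is a modest cost. The power target is already in SD units, and the plan concedes that the dietary score has no simple translation.

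**Conclusion.** No change to the plan follows. The endpoints, model, test level, sidedness and analysis population are fixed; what is missing is a normality criterion and a scale. The difficulty with the log largely resolves itself, because the rule offers an alternative that always exists.

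Under the assumed counts, each permitted analysis holds about 0.025, and so does a normality check made without regard to arm. Choosing by p-value would add on average 0.0332 − 0.025 = 0.008 and at most 0.0387 − 0.025 = 0.014 for the activity endpoint. That is a worst case with no support in the documents.

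Making the untransformed change primary would be a fair preference but not a correction: it gains 1-2 points of power in some models and loses 6 to 8.5 in others. Settling on the normalised change would close the gap equally well. Choosing one scale before comparing the arms is ordinary analyst practice.

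The sizes rest on assumed distributions. The validity of each single analysis depends less on them, since it held in every scenario tried with 250 per arm.

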We propose to conduct a randomized controlled trial investigating whether personalized lifestyle recommendations including genetic information motivates Hamilton Health Sciences employees to adopt healthy lifestyle changes. Study participation will be open to all Hamilton Health Sciences employees. Eligible and consenting individuals will be enrolled starting in March 2017. Enrollment will occur in a staggered fashion. The intervention group will receive (1) a free 3-month GoodLife Fitness gym membership providing access to any Canadian GoodLife Fitness facility, (2) professional trainer-approved workout plans, (3) dietitian-approved meal plans, and (4) genetic information pertaining to their health and fitness. The control group will also receive a GoodLife Fitness membership to ensure that all study participants are granted similar ease-of-access to perform physical activities but will not receive the personalized component of the intervention (workout plans, meal plans or genetic information) until the end of their trial period. Participants will be randomized to treatment or control groups using a minimization scheme for adaptive randomization, which will serve to balance age, gender, and ethnicity across groups as participants are enrolled. Thus, randomization will be performed in a single-blind fashion wherein the study team is unaware of whom is receiving the intervention or control. All study participants will be monitored over the course of 3 months beginning with their baseline assessment and ending with their 3-month follow-up assessment. At these two timepoints, study participants will be assessed for behavioural (physical

activity levels and diet healthiness) and biological markers (lipoproteins, fasting glucose, and inflammation) of cardio-metabolic disease.

Trial Population

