The 3-month follow-up assessment will be identical for participants assigned to either the intervention or control group and will consist of: (1) completing the exit study report form, (2) a blood draw which will provide biological material for laboratory testing, and (3) a low-risk fitness assessment which does not involve any physical activity (Table 2). The exit study report form will

strongly resemble the original baseline study report form and query information pertaining to demographics, medical history, dietary composition, physical activity levels, mental health and wellbeing, as well as attitudes, feelings, and competency regarding genetic testing. Laboratory testing will not include genetic testing (as this would be completed using the blood samples collected at baseline) but will include testing of lipoproteins, fasting glucose, and inflammatory markers as conducted in the baseline assessment.

To incentivize study participants to complete their final assessment, they will receive: 1) an additional month's worth of exercise and meal plans and 2) a lifetime subscription to the GeneBlueprint web portal which will be updated with new genetic prediction scores and health tools over time. Furthermore, individuals in the control group will be provided access to their genetic results, personalized meal plan, and personalized workout plan upon trial completion.

Endpoints

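### Filling missing 3-month outcomes with one mean pooled over both arms shrinks the treatment effect: with equal random loss m, the expected estimate is (1 − m) of the truth.

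*Combined protocol and SAP*

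**What the plan says.** - **Imputation rule (Data Analysis Plan, Technical Considerations).** Missing continuous values are "imputed based on the mean value across all samples with non-missing values including both intervention and control groups". The rule is not limited to baseline variables, and no other rule for missing outcomes appears in the documents. It is not stated whether the change score or the 3-month value is filled in.
- **Analysis set (Overview).** The plan adopts the intention-to-treat "principle to avoid biases due to differential adherence or loss-to-follow-up" and adds that "no post-hoc exclusions will be made".
- **Primary endpoints (Endpoints; Primary Endpoints).** These are changes from baseline to 3 months in physical activity and in dietary risk score, compared by linear regression at 0.025 each. "Weekly physical activity level will be represented as a continuous variable", so the rule applies to it. The data come from a questionnaire: "Physical activity levels will be quantified based on survey responses to the following questions".
- **Sample size (Power Calculations).** 250 per arm, 0.32 SD, 90% power, with no allowance for loss.
- **Retention (Final assessment).** "To incentivize study participants to complete their final assessment, they will receive" extra plans and a lifetime portal subscription. In addition, "individuals in the control group will be provided access to their genetic results, personalized meal plan, and personalized workout plan upon trial completion".

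**The concern.** The intention-to-treat statement is meant to protect the comparison from loss to follow-up. The imputation rule works against that aim. Each missing outcome is replaced by a value that does not depend on arm, so the missing participants show no expected difference between arms, and averaging them with the observed participants pulls the estimate towards zero. This happens even when loss is purely random, a situation in which simply analysing the observed outcomes would be unbiased.

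At stake are the primary estimates, the continuous secondary estimates and the 95% intervals that the Overview promises. An effect of the size the trial was planned to detect would be reported as smaller than it is, by an amount set by the attrition rate.

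**Working it through.** **Inputs.** 250 per arm, 0.32 SD and two-sided alpha 0.025 come from Power Calculations, Overview and Primary Endpoints. Every loss rate below is an assumption. So are reading 0.32 SD as SD of the change score and, in simulations, a baseline/follow-up correlation of 0.5.

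**The plan's own figure.** Normal approximation: 0.32 × √(250/2) = 3.578; power = Φ(3.578 − 2.241) = 90.9%. The noncentral t gives 90.8%. The stated 90% reproduces.

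**Equal random loss m.** Let μ₁ and μ₀ be the arm means and P the pooled observed mean. Each completed arm mean is (1 − m)μ + mP. On subtraction P cancels:

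expected difference = (1 − m)(μ₁ − μ₀).

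If the 3-month value is filled instead, the same algebra applies to follow-up means, and the baseline means cancel in expectation. The factor is the same.

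**Unequal random loss.** With retention r₁ and r₀, P = (r₁μ₁ + r₀μ₀)/(r₁ + r₀), and the factor is 2r₁r₀/(r₁ + r₀). For 10% against 30% loss: 2 × 0.9 × 0.7/1.6 = 0.7875, so 0.32 becomes 0.252.

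**Coverage when the change score is filled.** Bias = 0.32m; SE = √((1 − m) × 2/250). At m = 20%, bias = 0.064, SE = 0.080 and their ratio is 0.80, so coverage = Φ(1.16) − Φ(−2.76) = 87.4%.

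| Loss, both arms | Expected estimate (SD) | Plan's 50 MET-min/wk becomes | 95% CI coverage, change filled (formula) | 95% CI coverage, 3-month value filled (simulation) |
|---|---|---|---|---|
| 5% | 0.304 | 47.5 | 94.6% | 94.4% |
| 10% | 0.288 | 45 | 93.4% | 93.3% |
| 15% | 0.272 | 42.5 | 91.0% | 91.8% |
| 20% | 0.256 | 40 | 87.4% | 89.0% |
| 30% | 0.224 | 35 | 75.0% | 81.3% |

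Simulation (40,000 trials per setting) agrees with the formula column to about 0.2 points. The empirical SD matches the model SE (0.080 against 0.080 at 20% loss, change filled). The under-coverage therefore comes from bias, not from an understated SE.

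**Dependence on the true effect.** At 20% loss with the change filled, coverage is 93.1% for a true 0.16 SD and 95.0% for zero, with type I error 2.5% at alpha 0.025.

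**Effect on the test.** If the change is filled, estimate and SE shrink together: 0.256/0.080 = 0.32/0.100 = 3.2. Power then equals that of the observed-outcome analysis, about 83% at 20% loss. If the 3-month value is filled and the comparison is unadjusted, simulated power is about 73%. With baseline adjustment the two readings give similar power (about 91%).

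**Informative loss.** Assume 20% loss per arm, related to the change in the intervention arm only, with a log-odds slope of 1 per SD.

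| Who leaves the intervention arm | Plan, change filled | Plan, 3-month value filled | Imputation by arm and baseline | Truth |
|---|---|---|---|---|
| Poor responders | 0.39 | 0.33 | 0.45 | 0.32 |
| Good responders | 0.12 | 0.19 | 0.19 | 0.32 |

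**The case against.** **Attrition may be low.** No rate is given, and several features favour retention: follow-up lasts 3 months among one employer's staff, Table 1 excludes people planning more than 2 weeks of vacation and requires willingness for both fitness assessments and both blood draws, and completion is rewarded. Near 5% loss the bias is negligible. This stands and limits the severity. Against it, the core commitments named under Trial Population do not include the exit questionnaire, which supplies both primary endpoints.

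**Unequal loss is only a possibility.** Controls get their results and plans at trial completion, which may mean the end of the period and not attendance at the visit. That is fair. The direction is unknown, and the shrinkage does not depend on it.

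**The test may lose nothing.** This is true under random loss if the change score is filled. The harm is then confined to the estimate and its interval. Under the other reading the unadjusted test also loses power, and the plan does not say which reading applies.

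**The coverage figures depend on assumptions.** Also true. The plan's SD of 162.25 MET-min describes activity level, not change. If 0.32 is in SD of level, coverage at 20% loss with the change filled is about 90% at correlation 0.3 and 76% at 0.8. With baseline adjustment at 30% loss it is about 70 to 71%. If rank-based normalisation is applied after filling the change, the factor is about 0.88 at 20% loss and 0.81 at 30%, not 0.80 and 0.70. The plan does not give the order of these steps. All of these cases still shrink the effect.

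**Multiple imputation is not always closer to the truth.** The poor-responder case shows this. It is why a sensitivity analysis is needed, but it does not justify a rule that is biased even under random loss.

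**Conclusion.** The concern holds and should be fixed. As written, the rule multiplies a non-zero effect on any continuous outcome by (1 − m) under equal random loss, or by the harmonic mean of the two retention shares under unequal random loss. The factor assumes that no rank transformation follows the filling. The error is towards the null, with no added false positives under random loss. It is negligible near 5% loss and material at 20% or more, where a true 0.32 SD is estimated at 0.256 SD and the 95% interval covers about 87 to 89% of the time under the stated assumptions. If the rule was meant only for baseline covariates, the text does not say so, and the plan would then have no method for missing outcomes.

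**What to change.** 1. Limit pooled-mean filling to missing baseline covariates. There it is neutral between arms in expectation, because assignment follows the baseline assessment.
2. For missing 3-month outcomes, use multiple imputation conditional on arm and baseline value, combined by Rubin's rules and keeping everyone randomised. Baseline-adjusted regression on observed outcomes is an equally acceptable, simpler choice. State the missing-at-random assumption, and the order of imputation and transformation.
3. Add a delta-adjusted sensitivity analysis that shifts imputed values separately by arm, for example by 0, ±0.25, ±0.5 and ±0.75 SD of change. A shift in one arm moves the estimate by m × shift, or 0.05 SD per 0.25 SD at 20% loss. In the two informative scenarios, a shift of about ∓0.67 SD in the intervention arm restores 0.32 (0.45 − 0.2 × 0.67 and 0.19 + 0.2 × 0.67), so this grid spans both.
4. State that 90% power needs about 488 observed participants in the unadjusted change analysis, and give power by observed number: 90.8, 89.2, 87.4, 82.9 and 77.1% at 500, 475, 450, 400 and 350.

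**Check of the remedy.** In 1,500 simulated trials with 20 imputations within arm, estimates were 0.318 to 0.323 and coverage 94.3 to 95.5% at 5 to 30% equal loss. At 10% against 30% they were 0.321 and 94.2%. Baseline-adjusted regression on observed outcomes gave 0.321 and 94.3% at 20% loss (3,000 trials).

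**Cost.** SAP wording and a little R code. Intervals widen: at 20% loss the SE rises from 0.080 SD (change filled) to about 0.098 with multiple imputation and an unadjusted change comparison, or about 0.088 with baseline-adjusted observed outcomes. The missing-at-random assumption cannot be verified, and the new analysis is not better under every form of informative loss.
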